9.1 Event-adjudicating committee

The event-adjudicating committee is composed of a general cardiologist, a cardiologist with training in heart failure, and a general internal medicine specialist. The committee will meet at the end of the study and adjudicate all the events. The committee will be blinded to treatment allocation. In order to favor allocation concealment, the committee will also be blinded to C-reactive protein levels, which may be affected by treatment.

9.2 Definition of the events

The events adjudicated will include:

- Death;
- Cardiac death (in which a direct cause attributable to cardiac disease is present);
- Sudden cardiac death (in which cardiac death occurred out of the hospital and suddenly; or in the hospital due to ventricular arrhythmias unrelated to other concomitant cardiac conditions);
- Non-cardiac death (in which the event of death is considered not to be a direct consequence of cardiac disease);
- Incidence of heart failure during the index hospitalization (defined as dyspnea beginning or persisting >24 hours after admission and meeting both of the following criteria:
 - physical signs of heart failure including 2 or more of the following: edema, crackles/rales, jugular vein distention, hepatojugular reflex, tachypnea, rapid weight gain, S3 gallop, abdominal distension/ascites, radiologic evidence of worsening edema, pulmonary artery occlusive pressure (wedge) >18 mmHg or cardiac output <2.2 l/min-m²:
 - need for additional/increased heart failure therapy including one of the following: initiation or significant increase of oral diuretics, requirement of intravenous diuretics, inotropes or vasodilators, need for ultrafiltration due to decompensated heart failure;
- Re-hospitalization for any cause;
- Re-hospitalization for heart failure (meeting all criteria listed above for heart failure during index hospitalization)
- Incidence of heart failure (not hospitalized) defined as new or worsening dyspnea and meeting one of the two of the following criteria:
 - physical signs of heart failure including 2 or more of the following: edema, crackles/rales, jugular vein distention, hepatojugular reflex, tachypnea, rapid weight gain, S3 gallop, abdominal distension/ascites, radiologic evidence of worsening edema, pulmonary artery occlusive pressure (wedge) >18 mmHg or cardiac output <2.2 l/min-m²;

- need for additional/increased heart failure therapy including one of the following: initiation or significant increase of oral diuretics, requirement of intravenous diuretics, inotropes or vasodilators, need for ultrafiltration due to decompensated heart failure;
- Acute myocardial infarction, as defined by the WHO consensus statement
- Unstable angina, or need for coronary revascularization
- Cardiac tachy- or brady-arrhythmias leading to a new hospitalization or to prolongation of hospital stay;
- Acute renal failure (defined as in increase in plasma creatinine levels of 50% or 0.5 mg/L);
- Acute respiratory failure (not due to heart failure);
- Sepsis or other serious infection requiring antibiotic therapy;
- Acute stroke.

The analysis will consider time to first event and time to each event. It will also consider event rates at 3, 6 and 12 months, in order to favor comparisons with other studies. The number of days free of hospitalization during the first 1, 3, 6 and 12 months will also be measured and compared between groups.

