5.2 Secondary Exploratory Endpoints

Additional endpoints will include parameters measured at echocardiography, as well as biomarkers, and clinical outcomes.

Echocardiography: structural and functional echocardiographic parameters include left and right ventricular dimensions, mass, systolic and diastolic function. These will provide mechanistic insight as to whether the hypothesized changes in the acute inflammatory response will correlate with changes in cardiac dimensions or function. The echocardiogram will be ordered acutely (within 24 hours) and at 1-year follow up as clinically indicated.

Biomarkers: Blood will be collected at each time-point throughout the study (admission, 72 hours [or discharge whichever comes first], 2 weeks, 3, 6 and 12 months) and analyzed for complete blood cell count, metabolic markers (including lipids and lipoproteins, glycemic control and insulin resistance, liver and renal panel, sterols), inflammatory markers (i.e. high sensitivity CRP) and cardiac biomarkers (i.e. NT-proBNP and troponin I). The data will be collected and electronically stored for further analysis at the conclusion of the study. When feasible, results from clinically indicated studies will be used.

Clinical outcomes: Incidence of death (cardiac and non-cardiac), hospitalizations (for HF, for other cardiac causes not related to HF, or for non-cardiac reasons) will be recorded at each time-point throughout the study (discharge, 2 weeks, 3, 6 and 12 months) in every patient, and then once at the end of study, by review of chart and/or telephone interview. The investigators and clinicians caring for the patients will remain blinded to treatment allocation and to the CRP data. Adjudication of events will be performed by an *ad hoc* committee blinded to treatment allocation and to CRP data.

6) ENROLLMENT IN THE STUDY

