12.1 Study Hypothesis

We hypothesize that IL-1 blockade with anakinra will reduce the area-under-the-curve for CRP during the first 14 days with a greater reduction to be seen with high-dose anakinra, and that this will translate in more favorable cardiac remodeling and prevention of heart failure.

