 □ Acute Decompensated Heart Failure as primary diagnosis (see Protocol) □ Acute Coronary Syndrome as primary diagnosis □ Arrhythmia as primary diagnosis □ Acute Renal Failure □ Acute Respiratory Failure (not due to heart failure) □ Sepsis, or Severe Infection □ TIA/Stroke □ Other (Specify) 	 □ Out of hospital and sudden □ In-hospital, associated with ventricular arrhythmia not secondary to other cardiac disease □ In-hospital, associated with acute cardiac issue □ In-hospital, associated with acute non cardiac issue (Specify) □ Other (Specify) □ Unknown
Other events date	
(not leading to hospitalization)	ADVERSE EVENT: YES ☐ NO ☐
 □ Injection site reaction □ Rash □ Fever □ Infection (requiring antibiotic tx □) □ Nausea/Vomiting/Diarrhea □ Others: (Specify) 	ANTICIPATED □, NOT ANTICIPATED □ SEVERITY: MILD □; MODERATE □; SERIOUS □
Interruption of Treatment,	RELATED TO RESEARCH:
date ☐ Mandated by protocol ☐ Decision made by patient	UNRELATED □; POSSIBLY □; PROBABLY □; DEFINITELY □
	and RELATED TO RESEARCH → E PRINCIPAL INVESTIGATOR(s)
Completed By, Name Signature	Date
Attach de-identified Notes from chart or not	es (check if not available)
Principal Investigator(s) Signature	Date
Prompt report to the IRB/DSMB needed	completed D by on

	VCU-ART3 Ec	hocardioDoppler A	nalysis	
	Date S	ubject number:	Initials	
I I I I I I	ip as part of standard clini mages to be acquired on a neasurements. The study requires a Limite deemed necessary, then pro Measurements for research	cal care. The patient and digital format and then a digital format and then a digital format and then a digital format and ceed with full studypurposes do not need to didual center, they will be	rly as possible) and at 12 me Insurance may be billed for transferred to VCU for centr alysis – if a more complete e be performed on-line, neith performed single batch at t	: al lab exam is er need to
Ob	otain apical 4-chamber v	iew:		
	 Record 2 dimensio 	n imaging to measure	LVEDV and LVESV	
			o LVEDV / LVESV	
	 Record Color-Dopp 	ler of Mitral Inflow an	d Regurgitation	
			 Quantify regurgitation 	1
	 Record Color-Dopp 	ler of Left Ventricular	Outflow tract	
	 Record transmitra 	l Doppler flow spectra	E/ DT/ A	HR
	Record lateral wall	Mitral Annular tissue	Doppler spectra	
			E'lat/A'lat/ S'lat	
	 Record septum Mit 	ral Annular tissue Dop	pler spectra	
			E'sept/ A'sept/ S	s'sept
	 Record Tricuspida 	Annulus tissue Doppl	er spectra S'lat	
	 Record TAPSE (M-1 	node)	Excursion_	

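### On its plain wording, section 9.2 carries the index-stay 24-hour dyspnea rule over to heart-failure readmissions, so a readmission whose dyspnea clears within a day would not count as one

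*Combined protocol and SAP*

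**What the plan says.** Section 9.2 lists three heart-failure events.

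- **Index stay.** Dyspnea with a timing condition, "dyspnea beginning or persisting >24 hours after admission", together with both of two bulleted criteria: at least two listed signs or findings, and new or stepped-up heart-failure therapy.
- **Readmission.** No definition of its own, only a reference back: "Re-hospitalization for heart failure (meeting all criteria listed above for heart failure during index hospitalization".
- **Outside hospital.** "Incidence of heart failure (not hospitalized) defined as new or worsening dyspnea and meeting one of the two of the following criteria". This has no 24-hour element.

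The same list contains "Re-hospitalization for any cause". On use of the events, 9.2 says: "The analysis will consider time to first event and time to each event". It adds event rates at 3, 6 and 12 months and days free of hospitalization.

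Section 5.2, under secondary exploratory endpoints, records "hospitalizations (for HF, for other cardiac causes not related to HF, or for non-cardiac reasons". Section 12.1 hypothesizes, of the expected CRP effect, that "this will translate in more favorable cardiac remodeling and prevention of heart failure". The event form in Appendix C has a box for "Acute Decompensated Heart Failure as primary diagnosis (see Protocol", which points back to the protocol definition. Under 9.1 and 9.3, a committee blinded to allocation and to CRP adjudicates all events after the study is complete.

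**The concern.** In the index stay the 24-hour element has an evident use: it sets aside brief dyspnea that belongs to the STEMI presentation. In a readmission for heart failure, dyspnea usually precedes arrival and is the reason for it. The same element then asks whether dyspnea outlasted a day of treatment, which reflects response to treatment rather than whether heart failure was present.

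Heart-failure hospitalization is a named clinical outcome, and prevention of heart failure is part of the study hypothesis. If the committee applies the wording as it stands, some true heart-failure readmissions lose that label. If its members read the wording differently, similar stays may be classified differently.

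**Working it through.** No figure in the plan depends on this point, so the check is to set the definitions side by side and apply them to a test case.

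**Step 1. The three definitions in 9.2**

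| Event | Dyspnea element | Signs and therapy criteria needed |
|---|---|---|
| Heart failure, index stay | Begins or persists more than 24 h after admission | Both |
| Heart-failure readmission | By reference to the index stay | By reference: both |
| Heart failure, not hospitalized | New or worsening, no time limit | One of the two |

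**Step 2. Test case.** A patient is readmitted at month 2. Dyspnea began before arrival. Rales and edema are present (two listed signs), intravenous diuretics are given, and dyspnea is gone 20 hours after admission.

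- Signs criterion: met.
- Therapy criterion: met.
- Dyspnea beginning after admission: no, it began before.
- Dyspnea persisting more than 24 h: no, since 20 < 24.

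If every element of the index definition applies, the stay fails.

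**Step 3. Is there another place for the case?** The third category is labelled as not hospitalized, so an admitted patient does not fit it. Unless some other listed event also occurred, the stay is left under re-hospitalization for any cause and in days free of hospitalization, with no attribution to heart failure.

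**Step 4. Other readings of the reference**

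| Reading | Test case |
|---|---|
| All elements apply, timed from the readmission (plain wording) | Not counted |
| Criteria means only the two bulleted criteria | Counted |
| Admission means the index admission | Counted: dyspnea at month 2 began more than 24 h after that admission |

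The second reading also removes the dyspnea requirement from readmissions, because dyspnea stands in the lead-in and not in the bullets. Nothing else in 9.2, in 9.3 or on the event form chooses among the three. Taking the clause to mean dyspnea that begins at any time after admission does not help, because here it began before.

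**Step 5. Number of criteria by setting.** Take dyspnea with added heart-failure therapy and only one listed sign. Treated in clinic, one criterion is enough and the episode counts. Treated as an inpatient, both are needed and it does not. This difference remains under all three readings and is separate from the 24-hour element.

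**The case against.** The strongest reply is textual. In the heart-failure items of 9.2, the word criteria introduces the two sub-bullets each time, so the reference back may mean only those two. The 24-hour phrase also sits inside the index-hospitalization definition, so admission there may mean the index admission. Either reading rescues the test case. The choice of the word all rather than both leans the other way, but only weakly. This part stands: the exclusion follows from the plain wording and is not certain. It does not remove the point, because the text adopts neither lenient reading.

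A second reply is that the stakes are limited. The outcome is exploratory, the stay still counts as a re-hospitalization, and the event form asks for chart notes, so the committee could reclassify. That also stands. But reclassifying without a written rule leaves the definition to be settled once the events are in.

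A reader might go further in two directions that the documents do not support.

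- **A loss of power computed from the pilot heart-failure rates (30% vs 5%).** Those rates cover all new-onset heart failure, without a split by setting or a stated definition. The 24-hour element can remove only readmissions, and the share of these that resolve within a day is not given.
- **A treatment that moves care to the outpatient setting could appear to increase heart failure.** This needs an endpoint that pools inpatient and outpatient episodes, and 9.2 defines none. Such a shift would lower the heart-failure hospitalization outcome named in 5.2.

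**Conclusion.** The point holds as a defect of definition. Taken literally, 9.2 excludes heart-failure readmissions in which dyspnea began before arrival and cleared within a day, and no other heart-failure category takes them in.

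The direction is fewer counted heart-failure readmissions, with a risk of inconsistent classification. The size cannot be estimated from the documents. It depends on how many readmissions resolve that quickly and on which reading the committee adopts.

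The effect is confined to secondary exploratory outcomes. The primary endpoint (5.1) and the sample size (12.2) rest on CRP area under the curve and are untouched. The rule is the same in every arm and adjudication is blinded, so no bias between arms is shown. The different number of criteria by setting is a reason for care in pooling, not an error in itself.

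**What to change.** Before the end-of-study adjudication, while the committee is still blinded:

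1. State in 9.2 that the 24-hour element applies only to the index hospitalization.
2. Give heart-failure re-hospitalization its own definition: an admission with new or worsening dyspnea that meets both the signs and the therapy criteria, with no minimum duration after arrival.
3. Report hospitalized and non-hospitalized heart failure separately. If they are ever pooled, note that they require different numbers of criteria.

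Requiring both criteria outside hospital is optional. It would align the settings but would remove some events, which is a trade-off between sensitivity and specificity.

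The cost is a wording change in 9.2 and in the adjudication instructions. No new visits or data are needed, because the event form already asks for de-identified chart notes. The committee would no longer have to establish when dyspnea resolved in a readmission.

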6.2 Subject Inclusion and Exclusion Criteria

In order to be eligible for this study, patients must meet ALL the 3 Inclusion criteria and NONE of the Exclusion criteria.

INCLUSION CRITERIA:

- 1) Presentation to the hospital with acute STEMI defined as chest pain (or equivalent) with an onset within 12 hours and ECG evidence of ST segment elevation (>1 mm) in 2 or more anatomically contiguous leads that is new or presumably new
- 2) Coronary angiogram for potential intervention completed within 12 hours of symptom onset, and enrollment in the study within 12 hours of angiogram (max 24 hours from symptom onset)
- 3) Age>21 (NIH standard)

EXCLUSION CRITERIA:

- Inability to give informed consent
- Pregnancy or breastfeeding
- Preexisting congestive heart failure (AHA/ACC class C-D, New York Heart Association III-IV)
- Preexisting severe left ventricular dysfunction (EF<20%)
- Preexisting severe valvular heart disease
- Active infections (acute or chronic)
- Recent (<14 days) or active use of immunosuppressive drugs (including but not limited to high-dose corticosteroids [>1_mg/kg of prednisone equivalent], TNF-α blockers, cyclosporine) not including NSAIDs or corticosteroids used for IV dye allergy only)
- Chronic auto-immune or auto-inflammatory disease (including but not limited to rheumatoid arthritis, systemic lupus erythematosus)
- Known active malignancy of any type, or prior diagnosis in the past 10 years
- Anticipated need for cardiac surgery
- Active cancer (or prior diagnosis of cancer within the past 10 years)
- Neutropenia (absolute neutrophil count<1,800/mm³ [or <1,000/mm³ in African-American patients])
- Severe impairment in renal function (estimated glomerular filtration rate <30 ml/kg*min)
- Allergy to rubber or latex
- Allergy to products derived from Escherichia coli

7) STUDY DESIGN

We designed a multi-center, placebo-controlled, double-blinded randomized study of two different anakinra regimens (100 mg daily or 100 mg twice daily for 14 days). Patients will be enrolled and treated within 12 hours of coronary angiogram/angioplasty and within 24 hours of chest pain onset. A baseline echocardiogram will be ordered within the first 24 hours and repeated at 12 months, as clinically indicated. Biomarkers will be obtained at admission, 72 hours, 14 days, 3, 6 and 12 months.

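### Section 9.2 counts revascularization and any-cause re-hospitalization without excepting procedures already planned before the first dose, which dilutes the exploratory event analyses

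*Combined protocol and SAP*

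**What the plan says.** Protocol section 9.2 lists the events that the blinded committee will adjudicate. Two of them are "Re-hospitalization for any cause" and "Unstable angina, or need for coronary revascularization". Neither is limited to unplanned or ischemia-driven events, and no other section adds such a limit.

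On use of the events, section 9.2 states: "The analysis will consider time to first event and time to each event". It adds event rates at 3, 6 and 12 months, and then: "The number of days free of hospitalization during the first 1, 3, 6 and 12 months will also be measured and compared between groups". It does not say which of the listed items make up the first event.

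Heart failure appears in the same list as three items of its own: during the index stay, as a cause of re-hospitalization, and without hospitalization. Clinical outcomes as a whole sit under "5.2 Secondary Exploratory Endpoints", where hospitalizations are also recorded by cause.

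On timing, section 6.2 requires the angiogram first and allows enrollment up to 12 hours after it. The exclusion criteria remove patients expected to need cardiac surgery. They do not mention planned percutaneous procedures. The event form in Appendix C offers several reasons for hospitalization. None is a planned or elective admission, so one would have to go under the free-text 'other' line.

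**The concern.** When a patient is enrolled, the coronary anatomy is known and a second procedure for remaining lesions may already be decided. If that patient returns some weeks later for it, section 9.2 as written records a revascularization, a re-hospitalization and possibly the patient's first event. The cause is baseline anatomy, and the decision was made before the first syringe was given. A 14-day treatment cannot prevent it.

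Three analyses take in such events: time to first event, the rates of revascularization and of re-hospitalization, and hospital-free days. In each, events that treatment cannot change are added to both sides of the comparison. The ratio moves toward one, the absolute difference shrinks, and variance rises. Section 9.2 gives comparability with other studies as a reason for reporting event rates, and rates that mix planned with unplanned procedures serve that purpose less well.

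Sections 9.1 and 9.3 place adjudication at the end of the study. By then the committee would have neither a rule for planned procedures nor a dedicated field showing what had been planned.

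**Working it through.** **No stated figure to reproduce.** The plan gives no power or expected count for clinical events. Its only power statement, in the sample-size section, concerns AUC-CRP and does not depend on this point.

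**Inputs**
- Pilot any-cardiac-event counts (background section, the two pilots combined, N=40): 6 placebo and 3 anakinra patients, P=0.25. These events were death, recurrent infarction and new-onset heart failure.
- Patients per pilot arm: 20, implied by the percentages printed beside the counts (6 patients = 30%, 1 patient = 5%). The rates are then 6/20 = 30% and 3/20 = 15%.
- Trial size: 33 per arm. Significance level: two-tailed 0.025. Test for discrete variables: Fisher's exact. All come from the statistical section.
- Proportion s with a pre-planned procedure: **not in the documents**. Assumed 10%, 20% and 30%, equal across arms and independent of the other events.

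**Formula.** The proportion with any event is 1 − (1 − r)(1 − s), where r is the rate without planned procedures. The risk difference therefore becomes (r₁ − r₂)(1 − s).

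| s | Placebo | Anakinra | Risk difference | Relative risk | Fisher power |
|---|---|---|---|---|---|
| 0% | 30% | 15% | 15 points | 0.50 | about 15% |
| 10% | 37% | 23.5% | 13.5 points | 0.64 | about 10% |
| 20% | 44% | 32% | 12 points | 0.73 | about 7% |
| 30% | 51% | 40.5% | 10.5 points | 0.79 | about 5% |

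Example at s = 20%: placebo 1 − 0.70 × 0.80 = 0.44; anakinra 1 − 0.85 × 0.80 = 0.32; ratio 0.32/0.44 = 0.73.

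**Noise.** Plans made before allocation balance on average but not exactly. With 33 per arm, the standard deviation of the between-arm difference in the planned proportion is √(2s(1 − s)/33). That is 7.4, 9.8 and 11.3 percentage points at s = 10%, 20% and 30%, which is of the same order as the difference being sought.

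**Displacement of heart failure in time to first event.** If a share q of heart-failure events falls after the planned procedure, a fraction s × q of them is no longer the first event. With s from 10% to 30% and q from 25% to 75% (both assumed), this runs from 0.10 × 0.25 = 2.5% to 0.30 × 0.75 = 22.5%. In the analysis of time to each event, the heart-failure items lose nothing.

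**Limits.** Fisher power for a proportion stands in for a time-to-event comparison. The pilot rates are at 3 months, and the pilot event set is narrower than the full list in 9.2.

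**The case against.** The strongest reply is that the plan already protects what matters. Heart failure has three adjudicated items, each event type is analyzed by its own time, and hospitalizations are recorded by cause. This stands. A reader might infer from the missing exception that planned procedures hide heart-failure events generally. The documents do not support that: displacement is possible only in a first-event analysis across all items.

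A reader might also measure the loss from the pilot heart-failure rates alone, 30% against 5%. On that basis the relative risk goes from 0.17 to 0.39, 0.55 and 0.66, and Fisher power from about 60% to 35%, 23% and 15%. The arithmetic is right but the starting point is not. A first event across 9.2 includes death, infarction and more, and the pilots' any-cardiac-event figures put power near 15% before any planned procedure is counted. Most of that apparent fall comes from moving from heart failure to a broad composite.

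Three further replies have partial force:
- Clinical outcomes are exploratory and unpowered, so no stated figure changes. True, and it limits the weight of the point.
- The revascularization item could be read as new ischemic need, which a blinded committee could apply. Possible, but the text does not say so, and the forms give the committee no dedicated field for it.
- Any-cause re-hospitalization and hospital-free days are inclusive by definition. Fair. Keeping them as defined is legitimate if an unplanned-only version is shown alongside.

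The initial-assessment form has a broken tick-box beside PCI that may refer to staged procedures. The text is too damaged to rely on, and it stands among outcomes of the index stay. It shows neither that planned readmissions are expected nor that they are handled.

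**Conclusion.** The gap is real and narrow. Followed as written, section 9.2 would count as outcomes procedures fixed before the first dose. The consequence is attenuation and noise in exploratory analyses: time to first event, revascularization and re-hospitalization rates, and hospital-free days. Because the plans precede treatment and should balance on average, there is no ground to infer systematic bias for or against anakinra. The AUC-CRP endpoint, its sample size and the heart-failure-specific time-to-each-event analyses are untouched.

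The size cannot be fixed from the documents. At assumed rates of 10% to 30%, the any-cardiac-event relative risk weakens from 0.50 to between 0.64 and 0.79, and a power that is already low, about 15%, falls to between 10% and 5%. This rests on 20 patients per pilot arm, equal planned rates across arms, and independence from other events. Correcting the definition would make the first-event analysis cleaner. It would not make that analysis well powered.

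**What to change.** In section 9.2:
- State that a revascularization documented as planned before the first dose, and the admission for it, does not count in the revascularization item or in time to first event, and is listed separately by arm.
- State which events make up the first event.
- Keep any-cause re-hospitalization and hospital-free days as defined if preferred, and report an unplanned-only version of each beside them.

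In Appendix C:
- Add one yes/no item to the initial-assessment form: further coronary procedure planned before the first dose.
- Add a planned/unplanned item to the event form.

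The cost is a few sentences and two form items. Recording planned status at enrollment is more reliable than reconstructing it from charts at the end of the study. The downside is small: fewer counted events.

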7.7 Biomarkers assessment

Blood samples will be taken from a peripheral vein at admission, 72 hours, 14 days and 3, 6 and 12 months.

One EDTA-containing tube, one SST containing tube, one Serum Separator Clot Activator tube and one PPT tube will be used for analysis of plasma levels of biomarkers by the True Health Diagnostics LLC, Richmond, VA.

One sodium heparin tube will be used to analyze cytokines markers.

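### The absolute creatinine limb of the acute renal failure definition (0.5 mg/L, which is 0.05 mg/dL) is out of scale with the 50% limb and makes it inoperative

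*Combined protocol and SAP*

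**What the plan says.** Section 9.2 opens its list with "The events adjudicated will include" and includes acute renal failure, defined as an "increase in plasma creatinine levels of 50% or 0.5 mg/L". Either limb is enough. The definition gives no time window, no reference sample, no confirmatory sample and no accompanying clinical condition.

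On the use of these events, the same section says "The analysis will consider time to first event and time to each event". It adds event rates at 3, 6 and 12 months, partly so that results can be compared with other studies.

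Creatinine should be available throughout. Section 5.2 includes the renal panel among the analyses at each time-point ("glycemic control and insulin resistance, liver and renal panel, sterols"), and section 7.7 sets the schedule: "Blood samples will be taken from a peripheral vein at admission, 72 hours, 14 days and 3, 6 and 12 months".

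Appendix C captures the event twice, without a threshold either time. The event form has a box for "Acute Renal Failure" among the hospitalization reasons. The initial assessment form has a renal failure box among the in-hospital outcomes, with a sub-box for renal replacement. No other place in the documents gives a creatinine threshold or a different unit.

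**The concern.** Two limbs joined by *or* should describe roughly the same severity of injury, one suited to low baselines and the other to high ones. Here they differ about tenfold at an ordinary creatinine. The absolute limb is so small that it lies within the range of assay and day-to-day variation, and it makes the 50% limb redundant.

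This is the only written threshold for the event. A committee following it to the letter would have to classify small fluctuations as acute renal failure. In arms of about 33 patients, that could obscure genuine renal events in the time-to-event and event-rate summaries. It would also defeat the stated aim of comparability with other studies. A committee that silently reads a different unit would be departing from the protocol without a record.

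**Working it through.** The threshold is a definition rather than a derived figure, so there is no plan calculation to reproduce. The check has two parts. The first needs no assumption; the second does.

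**1. Unit and crossover (from section 9.2 alone)**

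- 1 L = 10 dL, so 0.5 mg/L = 0.5 / 10 = 0.05 mg/dL.
- The limbs are equal where 0.50 × baseline = 0.5 mg/L, that is, at a baseline of 1.0 mg/L = 0.1 mg/dL.
- At every higher baseline the absolute limb is reached first, so the 50% limb has no effect.

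**2. How often noise alone would meet the absolute limb**

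Inputs:

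- Five post-baseline draws: 72 hours, 14 days, 3, 6 and 12 months (section 7.7).
- Baseline creatinine *b* of 0.8 to 1.5 mg/dL (assumption; the documents give none).
- Total within-person coefficient of variation (CV) of 3% to 5% (assumption; the documents give none).
- Constant true creatinine, with independent normal errors of standard deviation *b* × CV.

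Formulas:

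- Relative size of the absolute limb: 0.05 / *b*.
- One baseline and one follow-up value: P = 1 − Φ(0.05 / (*b* × CV × √2)).
- Any of five follow-up values sharing one baseline: P = 1 − ∫ φ(z) Φ(z + 0.05 / (*b* × CV))⁵ dz.

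Example at *b* = 1.0 mg/dL for a single comparison:

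- CV 3%: 0.05 / (0.03 × 1.414) = 1.18, so P = 12%.
- CV 5%: 0.05 / (0.05 × 1.414) = 0.71, so P = 24%.

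| Baseline (mg/dL) | 0.05 mg/dL as % rise | One draw, CV 3% | One draw, CV 5% | Any of 5, CV 3% | Any of 5, CV 5% |
|---|---|---|---|---|---|
| 0.8 | 6.3% | 7% | 19% | 22% | 47% |
| 1.0 | 5.0% | 12% | 24% | 33.5% | 55% |
| 1.2 | 4.2% | 16% | 28% | 42% | 61% |
| 1.5 | 3.3% | 22% | 32% | 51% | 66% |

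Per arm of 33 patients (section on sample size), if all are followed with stable kidneys at 1.0 mg/dL, that is 33 × 0.335 ≈ 11 to 33 × 0.55 ≈ 18 patients.

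**Comparison**

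- An absolute limb of 0.5 mg/dL equals a 50% rise at 1.0 mg/dL. Under the same assumptions, noise would reach it in fewer than 0.001% of stable patients.
- The 50% limb on its own would likewise be met by noise essentially never.

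**The case against.** The strongest reply is that nobody is told to screen every scheduled creatinine against the rule. Renal failure enters through clinician tick boxes in Appendix C, one of them among hospitalization reasons, and three physicians then adjudicate events rather than laboratory series. A rise of 0.05 mg/dL in a well outpatient would not normally be ticked. This stands as a limit on impact, so the percentages above describe literal application and are not a forecast. It does not rescue the definition, because no text confines it to hospitalized or clinically recognized cases.

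The word *acute* might also be read as excluding late draws. With the 72-hour draw alone, the noise rate at 1.0 mg/dL is 12% to 24%, which is lower but still far too high for a renal failure event.

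Three stronger readings are tempting, and the documents do not support them:

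- **A reader might infer that most adjudicated renal events would be false positives.** That needs a true event rate, and none is given. These patients have had an infarction and angiography, so some small rises may be real.
- **A reader might infer that the time-to-first-event analysis is certainly distorted.** Section 9.2 does not say which events form it, and section 5.2 names only death and hospitalizations as clinical outcomes. The effect arises only if renal failure is included.
- **A reader might infer a spurious difference between dose arms.** The committee is blinded to allocation and to CRP, so misclassification should be mainly non-differential. Dilution is the more likely result.

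The documents also do not state that mg/dL was intended. That is an inference from the match between the two limbs.

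**Conclusion.** The definition is wrong as written. The unit conversion and the mismatch between limbs follow from section 9.2 alone: above a baseline of 0.1 mg/dL, only the absolute limb operates.

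The size of the consequence is conditional. It rests on the assumed baseline and CV, on literal application to all five post-baseline draws, and on independent errors around a stable level.

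What is affected is one exploratory adjudicated event: its time to event, its rates at 3, 6 and 12 months, and time to first event if renal failure is counted there. The primary endpoint (area under the curve for CRP) and the sample size built on it do not depend on this definition. Under section 9.3 the adjudication findings also have no bearing on trial conduct.

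**What to change.** Before the committee meets, the sponsor should:

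1. Confirm the intended unit of the absolute limb.
2. Correct section 9.2 so that the two limbs are commensurate. If mg/dL is confirmed, 0.5 mg/dL (5 mg/L) coincides with a 50% rise at 1.0 mg/dL.
3. Carry the same definition and unit to the Appendix C event form and to the in-hospital outcomes section of the initial assessment form, where renal failure now has no threshold.

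The documents list no separate adjudication charter, so the protocol and these forms are where the correction belongs.

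The cost is one unit in the text and a line on two forms. Sections 9.1 and 9.3 place adjudication after study completion, so a correction made before then requires no case to be re-adjudicated.
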